Blood pressure will be continuously monitored using a noninvasive device applied to the nonparalyzed arm or the right arm. The measurement intervals are as follows: every 15 minutes within the first hour post-randomization, every hour from 2 to 6 hours, every 6 hours from 4 to 24 hours, and then twice daily until day 7 (if the patient is discharged or dies before day 7, monitoring will be discontinued).

Given the clinical uncertainties regarding the potential benefits and risks, this study encourages adherence to the protocol but allows for adjustments to the treatment plan based on clinical needs. Nicardipine is recommended for blood pressure management, but other antihypertensive medications may be also selected according to the clinician's judgment.

Nicardipine injection administration protocol: dilute with saline or 5% glucose injection to prepare a solution containing 0.01–0.02% nicardipine hydrochloride (0.1–0.2 mg per 1 mL). Administer by intravenous infusion, starting at a rate of 2–10 μ g/kg body weight per minute. Once the target blood pressure is achieved, adjust the infusion rate while continuously monitoring blood pressure. If necessary, intravenous administration can be increased to a dose of 10–30 μ g/kg body weight per minute.

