7.1. Intensive blood pressure control group (experimental group)

The target blood pressure is <120 mmHg within 1 hour after randomization, and this level should be maintained for at least 48 hours. Intravenous antihypertensive treatment should begin immediately after randomization. A systolic pressure of 100 mmHg is the threshold for discontinuing both antihypertensive and vasopressor therapy. Oral antihypertensive agents may be used once blood pressure stabilizes. Care should be taken to avoid the occurrence of hypotension.

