7.2. Less intensive blood pressure control group (control group)

The target blood pressure is 140–180 mmHg within 1 hour after randomization, and this level should be maintained for at least 48 hours. Intravenous antihypertensive therapy is preferred. Antihypertensive agents should be used intravenously when systolic pressure exceeds 180 mmHg, and discontinued when systolic pressure is \leq 150 mmHg. Oral antihypertensive agents may be used

once blood pressure stabilizes. Even if systolic pressure drops below 140 mmHg, vasopressors should not be used unless hypotension occurs.

8. Outcomes

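### Above about 20 µg/kg/min, the permitted nicardipine escalation needs more fluid than the protocol's only stated solution can reasonably carry (9–18 mL/kg/h at 30 µg/kg/min)

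*Protocol*

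**What the plan says.** The dosing text is in Protocol section 7, Medication protocol. For preparation, sites are told to "dilute with saline or 5% glucose injection to prepare a solution containing 0.01–0.02% nicardipine hydrochloride", which the protocol also expresses as 0.1–0.2 mg/mL. For the start: "Administer by intravenous infusion, starting at a rate of 2–10" µg/kg per minute. For escalation: "If necessary, intravenous administration can be increased to a dose of 10–30" µg/kg per minute. The section gives no stronger solution for the escalated range, no ceiling on hourly volume, no time limit at the higher rates and no maximum total dose.

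The section also leaves clinicians room. On the choice of drug: "Nicardipine is recommended for blood pressure management, but other antihypertensive medications may be also selected". More generally, "this study encourages adherence to the protocol but allows for adjustments to the treatment plan based on clinical needs". Sections 7.1 and 7.2 add limits by arm. In the intensive arm, "A systolic pressure of 100 mmHg is the threshold for discontinuing both antihypertensive and vasopressor therapy". In the control arm, "Antihypertensive agents should be used intravenously when systolic pressure exceeds 180 mmHg", and they are stopped at 150 mmHg or below.

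**The concern.** Once a protocol fixes both the dose per kilogram and the concentration, it has also fixed the volume, whether or not it says so. Here the top of the dose range is three times the top of the starting range, but the solution stays the same. The implied volume is large for a patient with an acute stroke.

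What is at stake is safety rather than inference. Nicardipine is the recommended drug, and a site that follows the sentence literally at the top rate would give a large fluid load of saline or 5% glucose. Section 7.1 asks for intravenous treatment as soon as a patient is randomized to the intensive arm, whereas section 7.2 reserves it for pressures over 180 mmHg. Any use of the top rate would therefore be expected mainly in the experimental arm. How often it would happen cannot be known from the protocol.

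**Working it through.** **Inputs.** All come from Protocol section 7 except body weight. The protocol gives no weight, so 70 kg is assumed, with a range of 50–90 kg.

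**The protocol's own conversion.** 0.01% w/v is 10 mg per 100 mL, or 0.1 mg/mL; 0.02% is 0.2 mg/mL. The stated conversion is correct.

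**Volume per kilogram.** mL/kg/h = rate (µg/kg/min) × 60 ÷ 1000 ÷ concentration (mg/mL). No body weight is needed.

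| Rate (µg/kg/min) | mg/kg/h | mL/kg/h at 0.2 mg/mL | mL/kg/h at 0.1 mg/mL | mL/h at 70 kg |
|---|---|---|---|---|
| 2 | 0.12 | 0.6 | 1.2 | 42–84 |
| 10 | 0.6 | 3 | 6 | 210–420 |
| 20 | 1.2 | 6 | 12 | 420–840 |
| 30 | 1.8 | 9 | 18 | 630–1260 |

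**Range over weight at 30 µg/kg/min.** At 50 kg: 9 × 50 = 450 to 18 × 50 = 900 mL/h. At 90 kg: 9 × 90 = 810 to 18 × 90 = 1620 mL/h.

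**How long a litre lasts at 30 µg/kg/min and 70 kg.** 60,000 ÷ 630 = 95 minutes with the stronger solution; 60,000 ÷ 1260 = 48 minutes with the weaker.

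**Where the mismatch begins.** The protocol sets no volume limit, so the fairest internal yardstick is the largest volume its own starting range reaches: 10 µg/kg/min at 0.1 mg/mL, or 6 mL/kg/h. With the strongest stated solution, that volume delivers 6 × 0.2 ÷ 0.06 = 20 µg/kg/min. Rates up to 20 therefore stay within a volume the protocol already uses, provided 0.2 mg/mL is chosen. Above 20, neither stated solution does. At 30, the volume is 9 ÷ 6 = 1.5 times the yardstick with the stronger solution and 18 ÷ 6 = 3 times with the weaker. Staying at 6 mL/kg/h would need 1.8 ÷ 6 = 0.3 mg/mL, which is 1.5 times the strongest solution stated.

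**The case against.** The strongest reply is that nothing in the protocol is contradicted. The percentage conversion is right, the starting and escalation ranges meet at 10 µg/kg/min, and no volume limit exists to be breached. That stands: the yardstick above is a comparison made in this review, and whether the volume is workable is for clinicians to judge.

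A second reply is that 1260 mL/h pairs the highest rate with the weakest solution, when a site can choose 0.2 mg/mL and halve it. That also stands. Even so, the better case is 9 mL/kg/h, a litre about every 95 minutes at 70 kg.

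Third, escalation is conditional, the drug is not compulsory, other agents and clinical adjustment are allowed, and the stop thresholds apply. A site can stay at or below 10 µg/kg/min and be fully compliant. This limits the consequence, but the upper rate remains expressly permitted as written.

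A reader might infer more than the text supports:

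- **That the whole escalation range is unworkable.** It is not shown: up to 20 µg/kg/min the stronger solution fits within 6 mL/kg/h.
- **That tens of litres would be given over the 48-hour target period.** That assumes the peak rate is held throughout, which the protocol neither requires nor describes. The rate is to be adjusted once the target is reached.
- **That the per-minute unit is a slip.** The starting instruction speaks of a rate and the escalation sentence of a dose, which is a reason to check. It does not establish which element is wrong.

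**Conclusion.** The point holds in a limited form. With the only solution stated, the escalation above about 20 µg/kg/min exceeds any volume that the starting range implies. At the 30 µg/kg/min limit it needs 9–18 mL/kg/h, or 630–1260 mL/h at 70 kg and 450–1620 mL/h across 50–90 kg.

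The per-kilogram figures rest on the protocol alone, and the hourly totals rest on the assumed weights. The boundary at 20 µg/kg/min rests on taking 6 mL/kg/h as the volume the protocol already accepts. That higher volumes are unworkable is a clinical judgement, plainest near 30.

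A reader might go on to infer a bias between arms or a loss of power. The protocol does not support that: it gives no indication of how many patients would reach these rates, and nothing here bears on the primary outcome calculation. This is a minor safety correction.

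**What to change.** Check the 10–30 figure and its per-minute unit against the product's approved labelling, and correct the sentence in section 7. If the labelling supports a higher continuous rate, state the matching concentration beside it.

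Otherwise:

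- Limit the continuous infusion to 10 µg/kg/min. This is the highest rate that does not depend on the sentence in question.
- Specify the 0.2 mg/mL solution at the upper rates. At the limit this is 3 mL/kg/h: 150, 210 or 270 mL/h at 50, 70 or 90 kg.
- Direct sites to add or switch to another antihypertensive beyond that, as section 7 already allows.

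The cost is a one-sentence amendment and a re-issued dosing instruction to sites, with no extra patients or procedures. The downside is less room to escalate nicardipine alone, so some patients will need a second agent sooner.

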7.1. Intensive blood pressure control group (experimental group)

The target blood pressure is <120 mmHg within 1 hour after randomization, and this level should be maintained for at least 48 hours. Intravenous antihypertensive treatment should begin immediately after randomization. A systolic pressure of 100 mmHg is the threshold for discontinuing both antihypertensive and vasopressor therapy. Oral antihypertensive agents may be used once blood pressure stabilizes. Care should be taken to avoid the occurrence of hypotension.

7.2. Less intensive blood pressure control group (control group)

The target blood pressure is 140–180 mmHg within 1 hour after randomization, and this level should be maintained for at least 48 hours. Intravenous antihypertensive therapy is preferred. Antihypertensive agents should be used intravenously when systolic pressure exceeds 180 mmHg, and discontinued when systolic pressure is \leq 150 mmHg. Oral antihypertensive agents may be used

once blood pressure stabilizes. Even if systolic pressure drops below 140 mmHg, vasopressors should not be used unless hypotension occurs.

8. Outcomes

8.1 Primary efficacy outcome

Functional independence (90-day mRS score ≤ 2).

8.2 Primary safety outcomes

Rate of symptomatic intracranial hemorrhage (sICH), defined by the Heidelberg Bleeding Classification criteria [31];

All-cause mortality at 3 months.

8.3 Secondary efficacy outcome

mRS score 0–1 at 90 days;

mRS score 5–6 at 90 days;

Functional recovery, defined by 90-day mRS score improvement (shift analysis);

Infarct volume at 24 hours;

Change in infarct volume at 24 hours (compared to baseline);

NIHSS score at 24 hours;

Change in NIHSS score at 24 hours (compared to baseline);

24-hour NIHSS score 0–1 or improvement >8 points (%);

Change in NIHSS score at 7 days;

Brain edema volume at 7 days;

Health-related quality of life at 90 days (assessed by EQ-5D score).

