4.5 Privacy protection

Patients' medical records (study case records/CRFs, laboratory reports, etc.) will be securely stored at the hospital, with clinical test results well documented. Only the researchers involved in this study, the ethics committee, and regulatory authorities will be permitted to access the patient's medical records. Any public reports on the study findings will not disclose any patient identifying information. We will make every effort, within the bounds of the law, to protect the privacy of patients' medical data. In accordance with medical research ethics, except for personal privacy information, trial data will be accessible for public inquiry and sharing, limited to web-based electronic databases.

5. Sample size calculation

Based on published literature and clinical experience, the estimated 90-day functional independence rate (defined as mRS ≤ 2) in the control group is 35%. Using a two-tailed significance level of $\alpha = 0.05$, with 80% statistical power ($1-\beta = 0.8$), and a 1:1 allocation ratio between the experimental and control groups, we estimate that 376 participants per group are needed to detect a 10% improvement in the functional independence rate between groups. Considering a 20% dropout rate, a total of 910 subjects are needed to be enrolled, with 455 participants in each group.

Randomization will be performed using block randomization with block size of 10 (with at least 10 participants per center). For practical implementation, each center will be allocated a block, for example, if Center 1 plans to enroll 20 participants, blocks 1-2 will be allocated. This randomization scheme will be followed accordingly. If stratification variables are used, randomization will be performed within each stratum.

6. Randomization

Patients will be randomly assigned to two groups in a 1:1 ratio. Stratified block randomization will be used, with stratification by study center and intravenous thrombolysis. A 1:1 randomization

sequence will be generated. The randomization process will be managed using the "Jinling mouse" app.

7. Medication protocol

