9.1 Statistical analysis populations

Intention-to-Treat (ITT) Population: This population will include all randomized patients, regardless of whether they receive the intended intervention. A modified ITT analysis will be conducted based on the principle of the closest approach to the ITT population. Patients who withdraw consent before the blood pressure intervention, do not undergo the assigned procedure after randomization, lack endpoint data, refuse follow-up, or are lost to follow-up will be excluded from the statistical analysis. The modified ITT analysis will be used to evaluate the effectiveness and safety of the treatment regimen.

Per-Protocol (PP) Population: This population will exclude all patients with significant protocol violations, such as those who are under 18 years of age, have a final diagnosis other than acute ischemic stroke, have sustained systolic blood pressure <140 mmHg post-surgery, do not achieve reperfusion (mTICI <2b), have a pre-stroke mRS score of 3-5, lack 3-month follow-up data, or do not achieve the expected blood pressure control. The PP analysis will serve as a supplement to the modified ITT analysis.

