9.2 Statistical analysis methods

For continuous variables that follow a normal distribution, data will be presented as mean \pm standard deviation. For continuous variables that do not follow a normal distribution, data will be presented as median and interquartile range. Between-group comparisons will be performed using the independent t-test or Mann-Whitney U test. Categorical or ordinal data will be summarized using frequencies and percentages. For comparisons of categorical data between two groups, the χ^2 test or Fisher's exact test will be used; for ordinal data, the Mann-Whitney U test will be applied. All statistical analyses will be performed using SPSS software. A p-value < 0.05 will be considered statistically significant.

10. Study steps

After preliminary screening, patients who meet the criteria for endovascular intervention will undergo the procedure. Endovascular treatment methods include mechanical thrombectomy and aspiration.

[figure not shown]
At the end of the endovascular procedure, angiography will be used to assess successful reperfusion of the occluded vessel without in-situ or proximal arterial stenosis, with mTICI \geq 2b. Additionally, the patient's systolic blood pressure will be continuously elevated (\geq 140 mmHg, maintained for >10 minutes).

Randomization.

The intensive blood pressure control group will receive more intensive blood pressure management (target systolic blood pressure of 120 mmHg, achieved within 1 hour and maintained for 48 hours). The less intensive blood pressure control group will not have strict blood pressure control (target systolic blood pressure of 140-180 mmHg).

Follow-up and data collection.

11. Study schema

[figure not shown]

Figure 1. Study schema

12. Schedule of evaluations

Evaluation	Baseline (Prior randomisation)	Treatment phase		Follow-up phase
		1 day	7 days ^a	
Consent	X			
Eligibility	X			
Basic information	X			
Medical history	X			
Blood pressure	X	X	X	
mRS	X		X	X
NIHSS	X	X	X	
ASPECTS	X			
EQ-5D				X
Blood tests	X			
Menstrual history/urine pregnancy test (female)	X			
Electrocardiogram	X			
Details of rt-PA (if performed) and endovascular thrombectomy	X			
Brain imaging (CT ± CTA/MRI±MRA/DSA)	X	X	X	
BP lowering treatment		X	X	
Standard stroke care		X	X	X

SAEs	X	X	X	X
Complications		X	X	X
Completion status of research				X

Table 1. Experimental procedures and items to be assessed at each time point

a: Or the day of discharge (if the patient is discharged before day 7).

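### The exclusion of patients without endpoint data makes no exception for death, so 90-day EQ-5D and, less so, the 7-day NIHSS and oedema outcomes become survivor-only comparisons

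*Protocol*

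**What the plan says.** Section 9.1 defines a modified ITT analysis, used for both effectiveness and safety. Patients who "lack endpoint data, refuse follow-up, or are lost to follow-up will be excluded from the statistical analysis". Death is not mentioned there, and the protocol does not define what counts as endpoint data.

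Section 8.3 includes "Change in NIHSS score at 7 days", oedema volume at 7 days and "Health-related quality of life at 90 days (assessed by EQ-5D score)". None of these carries a value, rank or composite rule for a patient who died before the assessment. Five further NIHSS and infarct-volume outcomes are measured at 24 hours.

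Section 9.2 compares continuous outcomes by t-test or Mann-Whitney test and adds that "for ordinal data, the Mann-Whitney U test will be applied".

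Death is counted elsewhere: as mRS 6 in the mRS outcomes (sections 8.1 and 8.3) and as all-cause mortality, a primary safety outcome (section 8.2).

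**The concern.** A patient who has died has no NIHSS, no scan and no EQ-5D. With no value assigned and a rule that drops patients without data, the comparison is restricted to survivors. Survival is itself an outcome that treatment may change, so the survivors in the two arms need not be comparable even though the randomised groups were. If one arm loses more of its sickest patients, its survivors are a healthier selection and look better on these measures.

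The same dead patient would also be treated in opposite ways at the same time point: the worst outcome on the 90-day mRS, and absent from the 90-day EQ-5D. The two could then point in different directions for no reason other than deaths.

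**Working it through.** **Reproducing the plan's figure.** Section 5 assumes that functional independence "in the control group is 35"%, aims to "detect a 10% improvement in the functional independence rate between groups", and plans "with 80% statistical power" at two-sided 0.05.

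n = [1.96·√(2·0.40·0.60) + 0.8416·√(0.35·0.65 + 0.45·0.55)]² / 0.10² = 375.6, so 376 per arm. This agrees with the protocol and is the arm size used below.

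**Model (assumptions, not protocol figures).** Underlying health is standard normal with the same distribution in both arms, so treatment affects nothing but deaths. A proportion p die, namely those lowest on a frailty score that has correlation ρ with health. ρ = 1 means that exactly the sickest die; ρ = 0.5 is a looser link.

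With a = Φ⁻¹(p) and λ = φ(a)/(1 − p):

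- survivor mean = ρλ
- survivor variance = ρ²(1 + aλ − λ²) + 1 − ρ²
- d = difference in survivor means; SE = √[v₁/(376(1 − p₁)) + v₂/(376(1 − p₂))]
- chance of a significant false benefit ≈ Φ(d/SE − 1.96), nominally 2.5%

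**Worked case: 15% against 20% deaths, ρ = 1.**

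- λ = 0.2743 and 0.3500, so d = 0.0756 SD (0.076 before rounding error)
- variances 0.6405 and 0.5830; survivors 376 × 0.85 = 319.6 and 376 × 0.80 = 300.8
- SE = √(0.6405/319.6 + 0.5830/300.8) = 0.0628
- d/SE = 1.205, and Φ(1.205 − 1.96) = 22.5%

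**Range of cases.**

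| Assumed deaths | Shift in SD, ρ = 0.5 to 1 | False benefit by formula, ρ = 0.5 to 1 |
|---|---|---|
| 90 days, 15% vs 20% | 0.038 to 0.076 | 7.2% to 22.5% |
| 90 days, 15% vs 25% | 0.075 to 0.149 | 16.0% to 66.7% |
| 7 days, 6% vs 9% | 0.026 to 0.052 | 5.4% to 12.0% |
| 24 hours, 1.0% vs 1.5% | 0.006 to 0.012 | 3.0% to 3.6% |

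Simulating the Mann-Whitney test in survivors gives much the same: about 6% to 25%, 14% to 70%, and (at 7 days) 5% to 11%.

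**On the EQ-5D scale**, assuming mean 0.60 and SD 0.30, with 15% against 20% deaths and ρ = 1:

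- survivors only: 0.30 × 0.0756 = +0.023, an apparent benefit
- death scored 0: 0.80 × (0.60 + 0.30 × 0.3500) − 0.85 × (0.60 + 0.30 × 0.2743) = 0.564 − 0.580 = −0.016, a harm

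At ρ = 0.5 the two figures are +0.011 and −0.023. The sign reverses in both cases.

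**Effect of the remedy.** In simulation with ρ = 1 and the dead given the worst rank, false benefit falls to about 1.5% (15% vs 20%) and 0.5% (15% vs 25%).

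**The case against.** **The exclusion may not be aimed at the dead.** It stands in a list with refusal and loss to follow-up, so it may mean patients whose outcome is unknown. A dead patient has a known mRS of 6. On that reading the rule excludes no one for dying, and what remains is silence about secondary outcomes, which an SAP not shown could settle. This is a fair reading and it softens the point. It does not remove it: a dead patient kept in the population still has no EQ-5D or 7-day NIHSS to analyse, so the comparison in the protocol is survivor-only either way.

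**Higher mortality is not the expected result.** The protocol's introduction cites two trials with worse function under intensive control, and a reader might infer that more deaths should be expected. The same text reports no significant difference in 3-month mortality in one and in stroke-related mortality in the other. Worse function among survivors would also offset the spurious gain. This stands: unequal mortality is a risk to guard against, not a forecast.

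**The main results are protected.** With 376 per arm, a test of mortality has about 93% power at 15% against 25%, so a large spurious benefit would usually appear beside a visible harm. At 15% against 20% that power is only about 44%, so the protection is partial.

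**Stronger readings that the protocol does not support.** A reader might infer that the dead also leave the primary analysis. But sections 8.2 and 8.3 name mortality and mRS 5–6 as outcomes, which only makes sense if deaths are counted. A reader might also infer that every NIHSS and volume outcome is compromised. Five of these eight NIHSS, volume and EQ-5D outcomes are at 24 hours, when few patients will have died.

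**Conclusion.** The point holds for three secondary outcomes: mainly 90-day EQ-5D and, to a lesser degree, 7-day NIHSS change and 7-day oedema volume. The plan as written compares them in survivors, and with unequal mortality they can favour the arm with more deaths. It does not touch the primary outcome, the other mRS outcomes or mortality, and the 24-hour outcomes move by only about 0.01 SD.

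False significant benefit is about 6% to 25% at 15% against 20% deaths, about 14% to 70% at 15% against 25%, and about 5% to 11% at 7 days with 6% against 9%, compared with 2.5% nominal. These figures rest on assumed mortality, no effect on underlying health, and a frailty correlation of 0.5 to 1.0. The upper ends require that exactly the sickest patients die. With equal mortality, and deaths falling on the same kinds of patient in each arm, this model gives no bias.

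**What to change.** - In section 9.1, state that death is an outcome and does not count as missing endpoint data.
- For 90-day EQ-5D and 7-day NIHSS change, give patients who died before the assessment the worst rank and compare arms with the Mann-Whitney test already named in section 9.2. Report survivor-only values as supportive description.
- In the binary 24-hour NIHSS outcome, count death before the assessment as non-response.
- Report infarct and oedema volumes among patients imaged, labelled as descriptive and shown beside deaths by arm. Worst rank would turn an imaging measure into a composite with death, which is debatable and need not be required.

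The cost is wording only; sample size, visits and procedures are unchanged. The downside is that EQ-5D and 7-day NIHSS are then read as ranks that include death, not as mean differences. The change should be made before outcomes by arm are known, so that the handling of death cannot depend on the mortality seen. Label: cheap improvement.
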